1.1.2 Operational Definitions

First Aid Knowledge: Measured by a standardized questionnaire assessing participants' understanding of basic first aid principles, including recognition of injuries, appropriate responses, and the use of first aid equipment. A pre-test and post-test will be administered to evaluate knowledge gained from the training.

Practical Skills Proficiency: Evaluated through hands-on assessments where participants (children) demonstrate specific first aid techniques, such as identification of injuries including wounds and take action towards care. Proficiency will be rated on a scale from 1 to 5 by the trainers based on accuracy and confidence in performing the skills.

Training Attendance: Defined as the percentage of scheduled training sessions attended by each participant. Attendance will be tracked through a sign-in sheet at each

session, with a minimum attendance threshold set at 80% to qualify for the evaluation phase.

Behavioral Intent to Use First Aid: Assessed using a Likert scale survey administered after the training program, measuring participants' self-reported likelihood of applying first aid skills in real-life situations. This will include scenarios where they might encounter injuries or emergencies.

Community Engagement: Measured by the number of community members who give favourable feedback on the activities of the YoFA trainees during and after the intervention. The effectiveness of these activities will be evaluated through feedback forms from community members.

Self-Efficacy in First Aid: Evaluated using a self-report scale that assesses participants' confidence in their ability to perform first aid tasks taught. This will be measured before and after the training program to determine changes in self-efficacy levels.

Injury Response Time: Measured by timing participants' responses in simulated emergency scenarios during training sessions. The time taken to initiate appropriate first aid measures will be recorded and analyzed to assess improvement over the course of the program.

These will help us ensure that the study effectively measures the impact of the YOFA Training Program on early secondary school children in the Fako Division, providing clear metrics for evaluation and analysis.

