will be a session for pretesting at the beginning of the intervention, at the immediate end, and 3 months after. **During the 3 months follow up period, we will visit the schools during their Wednesday club days every 2 weeks for 30mins to 1hour, to document their experiences and challenges in real time and their use of the skills.**

The qualitative part will take place before the quantitative pretesting of both groups begins.

Table 6: Plan of training and Evaluation of intervention groups

HA	School	N	Training Period in 2024	Date for Last Evaluation, 2024
Molyko (Intervention)	BGS Molyko	25	Nov 6 th , and 13 th	Feb 5 th
		25	Nov 20 th , and 27 th	Feb 19 th
		25	Dec 4 th and 11th	March 5 th
Mutengene (Control)	GHS Mutengene	70	November 6 th	Feb 26 th
	Total	145		

Step 3: Evaluation Phase

This comprises the evaluation of students' perceptions, barriers, and challenges in learning and applying the skills and lessons learned. It will equally involve evaluating parents' and stakeholders' perceptions about the program and including FA training in school curricula. It will involve the use of evaluation forms. This will take place about the same time as the post-three-month evaluation.

Knowledge will be assessed by evaluating whether the participants have ever heard of first aid or observed situations in which first aid was needed. They will be expected to have an increase in knowledge of first aid, especially regarding calling for help, stopping acute and life-threatening bleeds (LTB), and referrals after the training.

Before the training, we expect people not to have practiced first acts ever or to have

done it in a wrong way or to be scared to carry out specific first aid acts. After the training, we expect them to be more alert and identify situations needing first aid acts. Additionally, we expect their self-efficacy and confidence to perform first aid acts to increase and to effectively carry out first aid acts within their community or the school premises that will be documented using designed forms.

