3.7 STUDY VARIABLES AND TYPE

Variables

Outcome variables

1. Knowledge Change: to determine whether or not there was an overall change in knowledge before and after the training (dichotomous).
2. Test scores: to measure the educational efficacy of the first aid training before and after the intervention in comparison with the control group (continuous)
3. Self-efficacy ratings: Participants' self-perceived efficacy in performing first aid skills or their confidence levels in "Stopping the bleed and/or calling for help" (dichotomous)

4. Response time: The time taken by participants to respond to simulated first-aid scenarios or emergencies that require them to either stop an LTB or call for help or refer (continuous).
5. The number of participants who make use of the skills taught during the 3 months post-training but before the final assessment (Discrete).

Exposure Variables

The exposure variables include training on LTBs from injury first aid and the use of these services by the trained students (e.g., the number of persons assisted or referred during the follow up period of the training).

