3.8 DATA COLLECTION TOOLS

A) Questionnaire

**Pre- and Post-Implementation of a Young First Aiders (YoFA) Training
Program Amongst Early Secondary School Children on Injury and Trauma
First Aid in Fako Division.**

Health District _____
Secondary School _____

Date: _____
Class: _____

A) QUESTIONNAIRE

Section 1

Please answer the questions below by **ENCIRCLING OR WRITING** the right answer you think is correct. If you do not know an answer, please select the answer you think is correct.

1. Gender	YES	or	NO
2. Age (in years):	_____		
3. Parents' Occupation:	Father _____ Mother _____		
4. Do you have access to a mobile phone all the time?	YES	or	NO
5. Have you heard the words First Aid?	YES	or	NO
6. Have you ever seen a traumatic injury? (A traumatic injury is an injury you sustain when something outside your body causes you to lose function or render you unable to use part or all of your body because of pain, bleeding or the because it is very serious)	YES	or	NO
7. A) Have you ever received any training in First Aid (formal or informal)?	YES	or	NO
B) If yes, briefly describe the training (where was it, what did you learn? How long ago was it?)			
Where? _____			
How long ago?			

 a) < 6months ago b) 6 to less than 12 months ago c) 1 to 3 years ago d) >3 years ago 			
What you learnt? _____			
<hr/>			
8. Have you ever seen someone bleeding and tried to stop that bleed yourself at home, school, marketplace, or anywhere else?	YES	or	NO
B) How many times has that happened? (Choose one)			

 a) Never b) Just once c) 2 to 5 times d) >5 times 			

C) What did you do to stop the bleeding? _____ **YES** or **NO**

D) Did it work? **YES** or **NO**

9. **A) Do you remember watching other people do this in the past?** **YES** or **NO**
B) Have you ever watched someone else offer such help in question 5? **YES** or **NO**

10. **If you find someone bleeding today,** **YES** or **NO**

A) Will you help them?

B) If 'no', why will you not help?

- I don't know what to do
- I am afraid I will make it worse
- I am afraid I will get into trouble
- I am afraid of blood
- Other reason _____

C) If 'yes', why will you help? _____

D) What steps will you take to help if 'yes'?

- Help by putting in toothpaste
- Help by applying pressure on the wound
- I will not help
- I will call an elderly person.

[figure not shown]
B) If you would not help, what makes you not want to help?

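### Response time has two different end events and no rule for pupils who never act, so comparing observed times alone can hide or reverse a training benefit on this outcome

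*Protocol*

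**What the plan says.** Section 3.7, outcome variable 4, is "The time taken by participants to respond to simulated first-aid scenarios or emergencies". It goes on to describe these as situations "that require them to either stop an LTB or call for help or refer (continuous", the last word being the variable type.

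Section 1.1.2, under Injury Response Time, gives the operational definition: "Measured by timing participants' responses in simulated emergency scenarios during training sessions". It adds: "The time taken to initiate appropriate first aid measures will be recorded and analyzed to assess improvement over the course of the program".

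Section 3.6, Step 3, expects that before training pupils will never have practised first aid, or will have "done it in a wrong way or to be scared to carry out specific first aid acts". After training, "we expect their self-efficacy and confidence to perform first aid acts to increase". The questionnaire in section 3.8 (item 10) allows for pupils who would not help, with reasons such as "I am afraid I will make it worse".

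The evaluation part of section 3.6 closes by promising that outcomes are compared between the intervention and control groups. Section 3.11 names a difference-in-difference analysis for changes in knowledge, attitudes and practices, and parametric and non-parametric tests for survey data. The protocol gives no scenario time limit and no value, rank or censoring rule for a pupil who does not act.

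**The concern.** There are two linked problems.

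First, the end events differ. Section 3.7 stops the clock at a response; section 1.1.2 stops it at the start of an appropriate measure. The people timing the scenarios need one definition.

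Second, a time exists only for pupils who reach the end event. Training is meant to raise the share who do. If only observed times are compared, the pupils entering the comparison are selected by something training changes. Pupils who would have done nothing untrained and who now act, perhaps hesitantly, add times to the trained side and have no counterpart on the untrained side. An improvement in the share acting then contributes nothing to the comparison, or counts against the programme.

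**Working it through.** **1. End events side by side**

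| Pupil in the scenario | Time under 3.7 | Time under 1.1.2 |
|---|---|---|
| Acts appropriately | yes | yes |
| Acts quickly but wrongly | yes, if any act is a response | none |
| Does nothing | none | none |

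The middle row is where the definitions can part. The last row is undefined under both.

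**2. The plan's own figure.** The protocol gives no figure for response time. Its only calculation (section 3.5) is for a proportion, 0.50 against 0.75, two-sided 5%, 80% power: (1.96 × √(2 × 0.625 × 0.375) + 0.842 × √(0.25 + 0.1875))² / 0.25² = 57.7, so 58 per group, as stated. It says nothing about response time. Everything below therefore rests on assumed inputs.

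**3. Break-even.** Let a share p₀ act untrained, with mean time m, and a share p₁ act trained. Habitual actors' times are multiplied by g, and newly acting pupils average x. The trained mean among actors is (p₀·g·m + (p₁ − p₀)·x) / p₁. Setting this equal to m gives x = m(p₁ − g·p₀) / (p₁ − p₀). With m = 40 s:

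- 50% to 75% acting, habitual actors 10% faster: 40 × (0.75 − 0.45) / 0.25 = 48 s
- 50% to 75%, habitual actors 25% faster: 40 × (0.75 − 0.375) / 0.25 = 60 s
- 90% to 95%, habitual actors 10% faster: 40 × (0.95 − 0.81) / 0.05 = 112 s

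If new actors average more than this, the observed mean worsens although nobody became slower. When nearly all pupils act anyway, the threshold is far out of the way.

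**4. Simulation.** 70 per group (Table 5). Assumed: log-normal times with log-SD 0.4, untrained actors' median 40 s (mean 40 × e^0.08 = 43.3 s), 180 s limit. The Welch test uses observed times only; the rank test places pupils without a time last. Percentages are the share of runs significant at 5%.

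| Share acting | Habitual actors | New actors' median | Observed mean, untrained / trained | Welch: gain | Welch: loss | Ranked last: gain |
|---|---|---|---|---|---|---|
| 50→75% | 10% faster | 70 s | 43.3 / 50.8 s | 0% | 34% | 56% |
| 50→75% | 10% faster | 52 s | 43.4 / 44.7 s | 1% | 6% | 71% |
| 50→75% | unchanged | 40 s | 43.4 / 43.3 s | 2% | 3% | 75% |
| 50→75% | 25% faster | 60 s | 43.3 / 43.1 s | 3% | 2% | 85% |
| 50→75% | 25% faster | 40 s | 43.3 / 36.1 s | 47% | 0% | 97% |
| 50→90% | 10% faster | 70 s | 43.3 / 54.7 s | 0% | 68% | 88% |
| 90→95% | 25% faster | 60 s | 43.4 / 34.2 s | 85% | 0% | 95% |
| 100→100% | 25% faster | none | 43.3 / 32.5 s | 98% | 0% | 98% |

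**5. Size in seconds.** A second set of assumptions: median 60 s among willing pupils, log-SD 0.6, 180 s limit, 50% willing before training and 90% after. The share acting in time is 0.5 × 0.966 = 48% before and 0.9 × 0.966 = 87% after. The mean among actors is 66 s both times. Counting pupils without an action at 180 s gives about 0.483 × 66.2 + 0.517 × 180 = 125 s before and 0.870 × 66.2 + 0.130 × 180 = 81 s after: a 44 s gain that the observed times do not show. With 80% and 95% willing, the observed mean again stays at 66 s, while the mean restricted to 180 s goes from 92 s to 76 s.

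**The case against.** No passage says that a mean is taken over acting pupils only. Continuous is a data type, a censored time is also continuous, and a statistical analysis plan that is not shown could supply the handling rule. That stands, so it would be wrong to infer that the protocol has fixed a faulty analysis. But a scenario limit has to be set before scenarios are run, and the end event has to be settled before anyone is timed. Section 3.11's non-parametric tests help only if pupils without a time are given a rank.

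A reader might also infer that Objective 3 will be answered with a null or the wrong sign. The documents do not support that. Table 7's indicators for Objective 3 are change in knowledge scores, stakeholder and student ratings, and the number of children using the skills; response time is not among them. Section 3.6 separately counts pupils who perform well in the scenarios.

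Nor does section 3.6 say that untrained pupils will be too scared to act. Fear of specific acts is one of three alternatives, and under 3.7 calling for help or referring also counts as a response. Section 3.7 names the required responses, so its conflict with 1.1.2 may be one of wording; the two still need one text.

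Section 1.1.2 places the timing in training sessions, and no timed untrained baseline is described, so the before-training shares above are hypothetical. Finally, letting all trained pupils be slower (median 70 s in the second set of assumptions) moves the actors' mean from 66 s to 74 s, but that slowing is put in by assumption. The reversal shown here rests only on cases where the newly acting pupils alone are slower.

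**Conclusion.** The point holds for the response-time outcome and no further. The two definitions should be reconciled, and as written a pupil who does not act, or under 1.1.2 does not act appropriately, has no time. Because the protocol expects wrong or fearful behaviour before training, comparing observed times only can understate or hide a benefit, or reverse it if newly acting pupils are slower. Under the assumed rise from 50% to 75% acting, the result ranges from a visible but weakened gain (47% of runs significant, against 97% with non-actors ranked last) to an apparent loss (34% significant for loss, none for gain). With 90% or more acting in both states the distortion is small. The shares acting, the times and the limit are all assumptions, so neither direction nor size can be predicted for this trial. It is worth correcting before data collection.

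**What to change.** - In sections 1.1.2 and 3.7, use one end event: the first appropriate action, as the programme itself defines it.
- Set a maximum scenario length before data collection and print it on the scenario sheet.
- In the between-group and before-after comparisons, treat pupils without such an action as censored at the limit, or rank them last.
- Report the proportion acting appropriately within the limit beside the time.
- State when control pupils are timed, since 1.1.2 places timing in training sessions.

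The cost is a few lines of text and one line on the scenario sheet. The downside is a summary slightly less familiar than a plain mean.

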3.8 DATA COLLECTION TOOLS

A) Questionnaire

**Pre- and Post-Implementation of a Young First Aiders (YoFA) Training
Program Amongst Early Secondary School Children on Injury and Trauma
First Aid in Fako Division.**

Health District _____
Secondary School _____

Date: _____
Class: _____

A) QUESTIONNAIRE

Section 1

Please answer the questions below by **ENCIRCLING OR WRITING** the right answer you think is correct. If you do not know an answer, please select the answer you think is correct.

1. Gender	YES	or	NO
2. Age (in years):	_____		
3. Parents' Occupation:	Father _____ Mother _____		
4. Do you have access to a mobile phone all the time?	YES	or	NO
5. Have you heard the words First Aid?	YES	or	NO
6. Have you ever seen a traumatic injury? (A traumatic injury is an injury you sustain when something outside your body causes you to lose function or render you unable to use part or all of your body because of pain, bleeding or the because it is very serious)	YES	or	NO
7. A) Have you ever received any training in First Aid (formal or informal)?	YES	or	NO
B) If yes, briefly describe the training (where was it, what did you learn? How long ago was it?)			
Where? _____			
How long ago?			

 a) < 6months ago b) 6 to less than 12 months ago c) 1 to 3 years ago d) >3 years ago 			
What you learnt? _____			
<hr/>			
8. Have you ever seen someone bleeding and tried to stop that bleed yourself at home, school, marketplace, or anywhere else?	YES	or	NO
B) How many times has that happened? (Choose one)			

 a) Never b) Just once c) 2 to 5 times d) >5 times 			

C) What did you do to stop the bleeding? _____ **YES** or **NO**

D) Did it work? **YES** or **NO**

9. **A) Do you remember watching other people do this in the past?** **YES** or **NO**
B) Have you ever watched someone else offer such help in question 5? **YES** or **NO**

10. **If you find someone bleeding today,** **YES** or **NO**

A) Will you help them?

B) If 'no', why will you not help?

- I don't know what to do
- I am afraid I will make it worse
- I am afraid I will get into trouble
- I am afraid of blood
- Other reason _____

C) If 'yes', why will you help? _____

D) What steps will you take to help if 'yes'?

- Help by putting in toothpaste
- Help by applying pressure on the wound
- I will not help
- I will call an elderly person.

[figure not shown]
B) If you would not help, what makes you not want to help?

11. **A) Is there a functional infirmary/dispensary/sickbay in your school?** **YES** or **NO**
B) Do you know where the closest/nearest health centre/hospital/clinic is to your house? **YES** or **NO**

12. **What will motivate (encourage/push) you to carry out a First Aid act to help someone in need? (Select all that apply)**

- Encouragement from your family to learn the FA skills and apply what is learnt
- Encouragement from your peers/friends/classmates
- What your neighbours, quarter head, or teachers think/say about you being a YoFA.
- You see it on social media or TV
- Getting more training
- You want to be a first responder
- Others. _____

13. **A severe/serious accident happens in front of you, and you must call an ambulance. What do you have to do? The pictures below show the actions you need to take, but they are in disorder. Rearrange them in order according to which one you will do first. Write the numbers 1 to 3 in the images according to what you will do first to what you will do last.**

14. **What would you do if your friend hurts his/her head lightly?**

- You immediately tell your friend to get up and continue your game.
- You put toothpaste on your friend's wound.
- You help your friend sit on a chair and ask if he/she is dizzy.

15. **What would you do if, while playing with your friend, he/she gets injured seriously/severely?**

- You help your friend get up.
- You run away to avoid punishment.
- You call for help and do not move him/her.

16. **What would you do if your friend injures his/her palm and the wound is slightly bleeding?**

- You apply pressure to the wound with a gauze pad or clean cloth.
- You wipe the blood with your hand.
- You apply toothpaste to the wound.

17. **When calling an ambulance, you must press/dial:**

- 118
- 117
- 119

18. **What should you say on the phone when you call an ambulance or call for help?**

- Your name and description of the accident.
- Describe the accident.
- Your name, the location of the accident, a description of the accident, and the number of injured people

Section 2:

“Life-threatening bleeding” (LTB) is an emergency. It is an injury or wound that should be cared for first because the loss of blood is great enough that the person will die if no first aid is given or delayed. Keep this in mind as you answer the following questions.

Meaning of some difficult words:

- **Spurting:** to flow out suddenly and with force, often in a fast stream
- **Streaming:** run or flow in a continuous current in a specified direction
- **Oozing or Trickling:** For a small amount of liquid to flow slowly out of something through a small opening or hole
- **Gushing:** flowing out suddenly, forcefully, or in large volume, as fluid that has been confined

[figure not shown]
This section is about being able to identify LTB (Life Threatening Bleeding) from a variety of descriptions (You can choose more than one answer)

19. Which of the following need immediate first aid to stop the bleeding:

a) Illustration of Blood oozing from scraped/scratched knee

b) Illustration of Blood spurting from arm

c) Illustration of Blood pooling on the ground

d) Illustration of Blood gushing from amputated foot

20. Which of the following does not need immediate first aid to stop the bleeding:

- a) Spurting/pulsating blood from the injury
- b) Streaming blood from the injury
- c) Oozing/trickling blood from injury
- d) Gushing blood from the injury

21. Which of the following need immediate first aid to stop the bleeding:

a) Photo of Scrape from a fall

b) Photo of full-thickness burn

c) Photo of Cut to thigh

d) Photo of Spurting blood from a forearm

22. Which of the following need immediate first aid to stop the bleeding:

- a) Blood spotting through one piece of gauze
- b) Blood-soaked clothing or bandages
- c) Bleeding that is not soaking through a bandage
- d) The overlying clothes are soaked in blood

23. Which of the following need immediate first aid to stop the bleeding:

- a) Pooling of blood on the ground
- b) Enough blood to fill 1/2 a soda can
- c) Two-tablespoons of blood from the injury on the ground
- d) A hole in the skin without flowing blood

24. **Which of the following need immediate first aid to stop the bleeding:**

- Dripping blood from a cut
- Gushing blood that will not stop coming out, even with a hand pushing on it
- Flowing blood from an injury that you are pressing on
- Blood spotting through several layers of cloth

25. **Rank the following: 1= at the top, most likely to die-- 4= at the bottom least likely to die**

- Bleeding from a person who is now unconscious
- Bleeding from a person who is not alert/not fully awake anymore
- Bleeding from a person who is now confused/not acting normally
- Bleeding from a person who is now pale

A tourniquet is a device that, when properly applied, stops blood from flowing by compressing blood vessels to a bone. [representative photos of a commercial Combat Application Tourniquet and an improvised tourniquet, both placed on a forearm]

26. **A tourniquet can be applied to a LTB in which of the following areas? (More than one answer)**

- Leg
- Arm
- Hand
- Stomach

27. **Which of the following need a tourniquet applied to save the life (one answer ONLY):**

- Scrape/scratch from a fall
- full-thickness burn
- Cut to thigh
- Spurting blood from leg

28. **A tourniquet may be required for an arm/leg that is partially or fully torn off.**

- a) True
- b) False

This next section is about the actions of using pressure and tourniquets to stop LTB.

29. **Climbing over a fence, a person cuts their stomach; it is bleeding and 3-4 inches (7-10cm) long. To control bleeding from this wound, you should:**

- a) Apply firm pressure with your hand directly where the bleeding seems to be coming from
- b) Apply a pressure dressing first, then apply manual pressure over the pressure dressing
- c) Apply an elastic bandage around the abdomen, ensuring that the wound is covered
- d) Apply a cold pack to the wound

30. **If you are alone with somebody who is not awake and has LTB coming from an arm/leg, what best describes your first action(s)?**

- a) Call for help on a cell phone
- b) Put a tourniquet on the injury
- c) Call for help while apply pressure or placing a tourniquet (i.e., speaker phone, yelling, activating alarm)

31. **Put the tourniquet above the wound so that it is between the torso/body and the wound.**

- a) True
- b) False

32. **After placing the tourniquet above the injury, it is critically important to tighten it as much as possible before turning the stick/rod.**

- a) True
- b) False

33. **You have applied a tourniquet to a LTB on a leg. The bleeding appeared to stop initially, but has now restarted. Which of the following should be the next step:**

- a) Apply a second tourniquet above the first (between the first tourniquet and the torso)
- b) Check to see if the tourniquet has loosened and tighten the tourniquet by turning the windlass/rod more
- c) Loosen the tourniquet, then reapply closer to the wound
- d) Remove the tourniquet completely and apply a different type of tourniquet
- e) Apply a second tourniquet directly on top of the first tourniquet

34. **If the person is in pain, the tourniquet is on too tight.**

- a) True
- b) False

35. **When should a tourniquet be removed?**

- a) A tourniquet should never be removed unless instructed by a physician or EMS provider
- b) When the patient begins experiencing severe pain
- c) When a first responder arrives on scene
- d) When bleeding has stopped

36. **When packing a bleeding injury, it is important to push material as close to the bleeding vessel as possible.**

- a) True
- b) False

37. **After packing an injury to stop bleeding, it is not necessary to apply pressure any more.**

- a) True
- b) False

38. **How excited are you about learning this training?**

- a) Not excited at all
- b) A little excited
- c) Excited
- d) Very Excited

B) FGD and in-depth interview Guide for teachers, Parents and administrators

Welcome dear parents/ teachers

We just introduced a plan to implement a First Aid Training program designed to teach 10 to 14 years old (forms 1 to 3) stop life threatening bleeds to avert complications and to build a first aid culture in them as they grow up. In order to improve this program and understand whether this will be a beneficial program in this community, we are asking you, the parents and teachers of the students at this level, to participate in a focus group discussion about the proposed project.

We want to understand your thoughts and concerns and hear your reactions to the project and to one another. We will ask you to sign a permission slip allowing us to record and transcribe the discussion, however, there will be no way to link what was said to you and your opinions will have no effect on your you or child, their grades, or any other consequence. We will use the data to strengthen the program and to help us decide whether training students is a good way to improve care for bleeding. This research is being done in conjunction with the University of Buea and University of California Los Angeles as well as the National Institutes of Health. Are there any questions? If you have any questions or concerns, please contact [name] at **[name]** anytime during or after the study.

I am turning the tape recorder on [CLICK]

Does everybody agree to participate in this interview?

1. First, what are your general impressions of the YOFA program as described?
2. What do you see as the benefits for children this age?
3. What do you see as the shortcomings of this program for children this age?
4. What do you see as the benefits or shortcomings of YOFA on the broader community?

How likely is it that a program using children this age will make the community safer / more prepared to face traumatic injuries?

Possible Barriers and Concerns

5. Are there any practical barriers or concerns to bringing the bringing YoFA training into schools among 10- to 14-year-olds? If yes, what are some of them? (That may be parental consent, curriculum integration, teacher training and student involvement).

6. How do you suggest these barriers/concerns might be overcome or improved?

Program design and delivery

7. What practical training parameters are important to you as a parent or teacher to make this training easy and safe to conduct? (Length, frequency & type of training)?
8. What role do you think parents and teachers should play in the implementation and ongoing support of the program?

Closing

Thank the participants for their valuable feedback and input.

Reiterate the importance of their perspectives in shaping the development of the "Stop the Bleed" young first aiders program.

Provide information on next steps and how the feedback will be used.

Interview Guide and FGD Guide for students

Opening of the interview with an ice-breaker question to put the students at ease, such as:"What are your thoughts on first aid training in schools?

1. What are your thoughts and feelings about starting a "stop the bleed" program for young first aiders in your school?
2. How do you think a program like this could help students your age, and what makes you feel that way?
3. What are some ways you think having classmates trained in basic bleeding control techniques could be helpful for everyone?
4. What worries or questions do you have about starting this program, and how do you think we could work together to solve them?
5. How do you imagine your friends would feel about the chance to become young first aiders, and what do you think might encourage or stop them from wanting to join?
6. In your view, what skills or information do you think are really important to include in the "stop the bleed" training for students like you?
7. What ideas do you have for making the program fun and interesting so that everyone wants to participate and learn?
8. How do you think having a "stop the bleed" program could change how your school thinks and acts about being prepared for emergencies?

C) ADAPTED SYSTEM USABILITY SCALE FOR THE YOFA TRAINING PROGRAM

Kindly indicate with the smileys below whether you think you will use the YoFA Skills learnt

1 = Strongly Disagree with the statement made	2 = Disagree with the statement made	3 = Neutral you neither agree nor disagree to the statement made	4 = Agree with the statement made	5 = Strongly agree with the statement made
 1 ☆☆☆☆☆	 2 ★★☆☆☆	 3 ★★★★☆	 4 ★★★★☆	 5 ★★★★★

ITEM	Value per 5-point Likert scale response, n (%)				
	1	2	3	4	5
1. I feel that I can know what to do with the YoFA skills if I see someone in need					
2. I found the skills taught too complicated to use.					
3. I thought the skills were easy to use.					
4. I think that I would need help from the staff to be able to use these skills.					
5. I found the training topics in the YoFA skill set to be strongly related/closely associated to each other.					
6. I thought there were too many changes/ups and downs in the skill set taught					
7. I would imagine that most other children of my age would learn to use these skills very quickly.					
8. I thought the skills were really hard to use.					
9. I felt very confident using the skill set.					
10. I needed to learn a lot of things before I could start applying the skill set					

